A Danish study from the Capital Region, in 2013 – the year before the medical helpline 1813 was introduced - found that 28% of the urgent consultations concerned 2.5% of the child population. These children had at least 4 urgent consultations yearly (6). Acute bronchitis was the most frequent diagnosis among these children, which were young (median age of 2.9 years), compared with all the children with an urgent contact (median age of 7.3 years) (6). Moreover, children with young mothers and children with immigrant parents had 37% and 28% increased risk for frequent contact (6), respectively.

A Danish study from the Capital Region, from 2014, the first year of the medical helpline 1813, showed that most calls concerned 0-1-year-old children who seldom exhibited serious conditions (7). The author interpreted the results as if the parents were primarily calling 1813 to get reassurance about the child's condition. When the children got older, the frequency of calls decreased, but in turn, they concerned more serious conditions (7).

Each year there are approximately 190,000 calls to the medical helpline 1813 regarding sick children younger than 12 years (injuries excluded) (8). These children are not so ill that the parents call the emergency helpline 112, but the parents need to contact the health care system outside their general practitioners' opening hours. After contact with the parents, the medical helpline 1813's health professionals may either: 1) refer the child to a paediatric department, 2) refer the

child to assessment in a paediatric urgent care centre (Børnelægevagten), 3) guide the parents to self-care at home, or 4) advised the child to their general practitioners (GP) the next workday.

In 2018, there were 192,000 calls about sick children (injuries excluded) (8). Of these calls, 57% children stayed at home the day the parents called 1813 (31% were guided in self-care and 26% were advised to their GPs the next workday), 40% were referred to the hospital (30% were referred to a paediatric urgent care centre and 10% were referred directly to a paediatric department) and 3% were referred to other options (8).

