Did the new material about sick children result in high parental self-efficacy among the parents who were allowed to watch the material?

Did new material about sick children result in less children examined by a doctor and more satisfied parents?

Primary outcome

Data of the electronic questionnaire from the parents;

High parental self-efficacy defined as parents who answered "i meget høj grad" or "i høj grad" to at least two of the three questions:

"Hvor godt kunne du passe dit syge barn hjemme, efter du søgte hjælp ved at ringe 1813?",
"Ved du hvad du kan gøre hjemme, hvis dit barn får samme symptomer en anden gang? and
"Ved du, hvornår det er så alvorligt, at du skal kontakte læge eller 1813, hvis dit barn får samme
symptomer en anden gang?"

Secondary outcomes

Data of the electronic questionnaire from the parents;

- Use of professional consultations: Yes to the question "Har en læge/sygeplejerske undersøgt dit barn under dette sygdomsforløb?" (både egen læge og læge på hospital).
- Satisfied with the contact to the acute telephone 1813: Yes (svar "i meget høj grad" og "i høj grad") to the question "Er du overordnet tilfreds med den hjælp du fik, da du kontaktede 1813?"

Exploratory outcomes

Data of the electronic questionnaire from the parents;

- The medical status of the sick child "Hvordan har dit barn det nu, sammenholdt med da du kontaktede 1813?"

Data from the Copenhagen Emergency Services;

- The number of telephone contacts to 1813, the age and the sex of the child.
- The number of parents who called 1813 within the next 72 hours after the initial call.
- The number of patients, who were referred to a hospital within the next 72 hours after the initial call.

Data of the calls from the videos and action cards;

- The number of times the 8 videos and the eight action cards were used within the next 72 hours after initial contact to 1813.
- The duration and types of videos and action cards the parents watched within the next 72 hours.

Data from the case reports from Epic (Sundhedsplatformen);

- The number of patients, who went to a hospital within the next 72 hours after the initial contact to 1813, and the time of arrival.
- The number and diagnoses of patients who did neither get treatment nor paraclinical tests, but merely parental medical at hospital.
- The number and diagnoses of patients who went home from the hospital with treatment for example antibiotics or painkillers.

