- The number of number and diagnoses of sick children who were inpatients in less than 12 hours, more than 12 hours, more than 24 hours in the following 72 hours or went to the intensive care unit.

Automatic speak when the parents call 1813 and the SMS-questions the next day

Please notice **Appendix 1**, in Danish, for specific information.

Safety measures: The paediatric departments in the Capital Region will be made aware of the study. The case reports of the included children at the hospitals will be reviewed within 3 to 8 days after the call. This will primarily be done by the ph.d. student doctor, who is blinded for the information of the study group (intervention versus control group). We will register the number of children who went to departments of Paediatrics, the diagnosis, the duration of hospitalization, intensive care admittance and mortality within 72 hours after the call. It will also be noted, if there are cases of unexpected serious adverse events, near-misses, death, and if it looked as if the child went to hospital later than optimal based on parental delay. In these cases, this information will be presented for a **Data Safety Committee** and it will be revealed if the child was randomized to the intervention or to the control group. The **Data Safety Committee** will advise the study group on continuation, modification, or stopping the trial.

Sample size

We want to be able to detect if the intervention with videos and action cards increases the proportions of parents who expressed high self-efficacy by 5%. We do not know this actual proportion. If it is actual 50%, we want to detect an increase to 55%. We want a p-value of 0.05 and a probability (power) of 80%.

It will require data from about 3300 text-messages (SMSs) in total, randomized in two equal groups (<http://www.openepi.com/SampleSize/SSCohort.htm>).

If the baseline is at a higher level, for example 70% then we want an to be able to detect an increase to 75%, and with the same p-value and power we then require totally 2520 SMSs.

There are about 160.000 calls concern children of at least 6 months of age to the medical helpline 1813 (18).

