If we suggest that 25% of the parents to the sick children agree to be randomized, and that 40% of the included parents answers the text-message the next day, then we can include $(160,000 \times 0.25)/365 =$ about 110 children a day, and we will get about 44 text-messages a day. Then we need $2520/44 - 3300/44 = 57- 75$ days to include enough patients. It is less than 3 months.

In the data from the Copenhagen Emergency Services, and data from the safety measures we will not have loss to follow up, since data from the Copenhagen Emergency Medical Services and from all four Departments of Paediatrics in the Capital Region are collected routinely.

In the data of the calls from the cases we also suggest that all contacts are safety stored so we will have no loss to follow-up.

We suggest we have data to answer our research question within 3 months, and the study will be stopped after 6 months.

Stop of the study before an answer our research question

In cases of serious adverse events the study group will consider stopping the study. This will also be the case if the satisfaction with the contact to the acute telephone 1813 drops to a very low level.

Statistics

The primary analysis will use Chi-square and a two-sided level of significance of $p < 0.05$ for the primary outcome and a $p < 0.025$ for the two secondary outcomes. All other outcomes are exploratory and the statistical methods will be adapted as appropriate. The results from these exploratory analyses will not be used to claim clinical efficacy but used to design new studies. This is an important aspect since new studies can be rapidly designed and performed once the project set-up is in place.

The dataset will be rich and allow exploration of the effect of individual videos, as well as subgroup analyses.

We believe that our set up is robust, as the sick children are included based on electronic equipment, not adding extra work on the medical personnel, the operators. The follow up to the parents by text message the next day is also based on electronic equipment and the follow-up in the medical case reports after 72 hours, for safety reasons, is based on easily available information, if we have the relevant permits for this.

Ethics and transparency

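### The primary chi-square is valid but makes no use of child age and sex; a prespecified adjusted risk difference would be a modest, nearly free improvement

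*Combined protocol and SAP*

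**What the plan says.** All references are to the combined protocol and SAP.

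- **Statistics.** "The primary analysis will use Chi-square and a two-sided level of significance" of 0.05 for the primary outcome, with 0.025 for each of the two secondary outcomes. The text names no covariate, stratification factor, adjusted model, effect estimate or confidence interval.
- **Exploratory outcomes.** The data from the Copenhagen Emergency Services include "The number of telephone contacts to 1813, the age and the sex of the child". Age and sex are therefore listed among outcomes, although they are fixed before allocation and age is also an eligibility criterion.
- **Sample size.** The protocol expects no loss to follow-up in the Emergency Services data. It assumes that "40% of the included parents answers the text-message the next day", so about 60% of randomised families would have no primary outcome.
- **Set up.** Age and sex are to be examined to see whether bias was present, and to compare families who accepted with those who declined. No comparison of repliers by arm is named, and no correction is stated if an imbalance appears.
- **Ethics and transparency.** The interim look at 400 replies checks whether the number of replies is similar in the two arms. It does not check whether their composition is.

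**The concern.** Two things are left unused. First, a covariate that predicts the outcome reduces the standard error of the treatment comparison, and these two are already in a routine source. Second, the chi-square is run on repliers only. Randomisation balances age and sex among all allocated families, but it does not guarantee balance among those who answer. The arms also have different contact with the helpline: according to the Danish summary, intervention parents must ring 1813 again to speak to a nurse or doctor, whereas control parents speak to one as usual. Reply that differs by arm is therefore conceivable.

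The background section gives indirect reason to think age might matter. It reports that most calls concerned infants who were seldom seriously ill, and adds: "When the children got older, the frequency of calls decreased, but in turn, they concerned more serious conditions".

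The protocol already treats age and sex as possible sources of bias but attaches no consequence to what it finds. Any adjustment would then be chosen after the data had been seen, including the effect analysis planned at 1000 replies. Finally, the target is a 5-point increase, whereas a chi-square by itself returns only a p-value.

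**Working it through.** **Inputs from the documents (Sample size).** Two-sided alpha 0.05, power 80%, 1:1 allocation. For 50% versus 55%: "It will require data from about 3300 text-messages (SMSs) in total, randomized in two equal groups". For 70% versus 75%: "we then require totally 2520 SMSs".

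**Assumed inputs.** The documents do not give the share of outcome variance explained by age and sex (R²), the self-efficacy gap between age groups, or the age mix of repliers. Ranges are shown below.

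**1. Reproduce the plan's figures.** Per arm, n = [1.96·√(2p̄q̄) + 0.842·√(p₁q₁ + p₂q₂)]² / (p₂ − p₁)².

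- 50% versus 55%: total 3130, or 3210 with continuity correction. The stated 3300 is within 3% of the latter.
- 70% versus 75%: total 2502, or 2582 with correction. The stated 2520 fits either.

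The stated sizes are thus consistent with an unadjusted two-sided comparison of two proportions.

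**2. Precision.** Adjustment multiplies the variance of the risk difference by about (1 − R²), so the effective sample size is N/(1 − R²).

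| Assumed R² | SE factor √(1 − R²) | Extra replies, 3300·[1/(1 − R²) − 1] | Power at 3300, 50% vs 55% | Power at 2520, 70% vs 75% |
|---|---|---|---|---|
| 0 | 1.000 | 0 | 82.0% | 80.3% |
| 0.01 | 0.995 | 33 | 82.4% | 80.7% |
| 0.02 | 0.990 | 67 | 82.8% | 81.1% |
| 0.05 | 0.975 | 174 | 83.9% | 82.3% |

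**3. What R² is plausible?** For a two-group age split with share s in the younger group and outcome gap g, near a 50% rate, R² = s(1 − s)g²/0.25.

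- A 15-point gap gives 0.16 × 0.0225/0.25 = 0.014 at s = 20%, and 0.25 × 0.0225/0.25 = 0.023 at s = 50%. That is worth under 1 point of power.
- R² of 0.05 with an equal split needs g = √0.05, or about 22 points.

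**4. Imbalance among repliers.** Shift in the crude difference = (between-arm difference in age mix) × (outcome gap).

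- Chance SD of the difference in age mix with 1650 repliers per arm is √(2s(1 − s)/1650): 1.4 points at s = 20% and 1.7 points at s = 50%.
- One SD with a 15-point gap shifts the estimate by 0.014 × 15 = 0.2 to 0.017 × 15 = 0.3 points.
- A 5-point difference in age mix with the same gap gives 0.05 × 15 = 0.75 points, which is 15% of the 5-point target. But 5 points is 5/1.7 = 2.9 to 5/1.4 = 3.6 chance SDs. It would in practice require reply that depends on age differently in the two arms.
- If a systematic shift of 0.75 points did occur, the SE under the null is √(0.25 × 2/1650) = 1.74 points, the shift is 0.75/1.74 = 0.43 SE, and the two-sided type I error would be about 7%.

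**The case against.** The case for leaving the plan alone is strong in several respects.

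- **The test is valid.** A two-sided chi-square on a binary outcome after 1:1 randomisation is standard and matches the sample-size method. Its type I error already allows for chance imbalance. This stands: nothing in the documents makes the choice an error, although a reader might infer that it is one.
- **No association is documented.** The background statement on age concerns the frequency and seriousness of calls. It does not concern self-efficacy or reply behaviour, and nothing is offered for sex. A reader might take it as showing that age predicts the primary outcome; it does not. R² could be zero, in which case nothing is gained.
- **The 0.75-point shift is a constructed scenario.** A reader might infer that the crude result is likely to be off by 15% of the target. Chance does not produce that, and the documents give no evidence of reply that depends on age differently by arm. It remains possible, because 60% are expected not to reply and the arms have different contact with 1813.
- **The main threat is non-reply itself.** Reply may depend on satisfaction, severity or the help received. Adjustment for age and sex corrects none of these directly, and an adjusted primary analysis must not be read as having dealt with them.
- **The effect size needs no model.** A crude risk difference with a confidence interval comes from the same 2×2 table. This is correct, so the missing estimate does not by itself argue for changing the primary test.
- **Anonymisation.** Ethics and transparency promises complete anonymisation, and adjustment needs each reply linked to its call record. Set up already describes family-level data on further calls, hospital records and use of the material, so linkage before anonymisation appears feasible.

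These points reduce the size of the concern. They do not remove the case for a prespecified adjustment with data already held.

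**Conclusion.** The point holds as a recommended improvement. The primary analysis leaves unused two baseline variables from a source described as complete, and the plan's own bias check has no analytic consequence.

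The benefit is modest. It is about 0.4 to 2 points of power at 3300 replies for an assumed R² of 0.01 to 0.05, and nil at R² of 0. Power at the stated sizes already meets the 80% target without adjustment. Protection against imbalance is worth about 0.2–0.3 points per SD of chance imbalance, given an assumed 15-point outcome gap. It is worth more only if reply depends on age differently by arm. Adjustment removes only the part of reply bias that runs through age and sex. All these sizes rest on assumed associations, because the documents supply none.

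**What to change.** In Statistics, prespecify as the primary analysis a logistic regression of high self-efficacy on arm, child age and sex. Standardise it over the repliers to an adjusted risk difference with 95% CI, tested at two-sided 0.05. State in advance how age enters the model. Use the same model for the two secondary outcomes at 0.025. Keep the chi-square and the crude risk difference with its confidence interval as supporting analyses. Tabulate age and sex by arm and reply status, so that the bias check in Set up covers the analysed set. Say explicitly that the adjustment does not address non-reply beyond age and sex.

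The cost is a short paragraph and a few lines of code, with no new data collection. The primary analysis becomes slightly less simple, and SMS replies must be linked to the call records before the data are anonymised.

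### Testing each secondary outcome at a fixed 0.025 is valid but inefficient: Holm's procedure keeps the pair's 5% bound and can detect the second outcome more often

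*Combined protocol and SAP*

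**What the plan says.** The Statistics section specifies a chi-square test with a two-sided level of 0.05 "for the primary outcome and a $p < 0.025$ for the two secondary outcomes". It then states: "All other outcomes are exploratory and the statistical methods will be adapted as appropriate". The confirmatory secondary family therefore has exactly two members, both listed under Secondary outcomes and both taken from the text-message questionnaire:

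- whether the child was examined ("Use of professional consultations: Yes to the question" about examination by a doctor or nurse);
- satisfaction with the helpline ("Satisfied with the contact to the acute telephone 1813: Yes", meaning one of the two highest answers).

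The documents contain no step-down rule, ordering, gate or recycling of alpha. The Sample size section sets a power target for the primary outcome only. It asks for about 3,300 replies if the baseline proportion is 50% and 2,520 if it is 70%, in two equal groups. No expected rate, effect or correlation is given for either secondary outcome.

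**The concern.** Under a fixed 0.025 per test, a secondary outcome with a p-value between 0.025 and 0.05 is declared not significant however strong the result on the other one. With p = 0.001 for examinations and p = 0.03 for satisfaction, for example, only the first could be claimed. Holm's procedure would allow both claims with the same family-wise guarantee for the pair.

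This bears on the trial's own question. The second part of Aim of the study asks about fewer examined children together with more satisfied parents. Power to show both is therefore a relevant quantity, and it is where the fixed split costs most.

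**Working it through.** **Inputs.** From the documents: two secondary tests at 0.025 each (Statistics); 3,300 or 2,520 replies in two equal groups, so n = 1,650 or 1,260 per arm (Sample size). Assumed, because the documents are silent: examined 40% to 35%, satisfied 70% to 75%, two-sided tests, and correlation 0 to 0.5 between the test statistics.

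**The plan's own figures.** 0.05/2 = 0.025 and 0.025 + 0.025 = 0.05, so the stated level is a Bonferroni split. The reply counts are taken as given. At a two-sided 0.05, the power for 50% against 55% with 1,650 per arm is 82.0%, and for 70% against 75% with 1,260 per arm it is 80.3%. Both are consistent with the 80% target.

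**Holm's rule.** Compare the smaller p-value with 0.025. If it is significant, compare the larger with 0.05.

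**Power of a single test.** The mean of the z-statistic is |d| / √(2p̄(1 − p̄)/n). At n = 1,650:

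- examined: 0.05 / √(2 × 0.375 × 0.625 / 1,650) = 2.966;
- satisfied: 0.05 / √(2 × 0.725 × 0.275 / 1,650) = 3.216.

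At n = 1,260 the means are 2.592 and 2.811. The critical values are 2.241 (level 0.025) and 1.960 (level 0.05). Write a for power at 0.025 and b for power at 0.05.

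| Replies | Outcome | a | b |
|---|---|---|---|
| 3,300 | examined | 0.7658 | 0.8429 |
| 3,300 | satisfied | 0.8352 | 0.8955 |
| 2,520 | examined | 0.6372 | 0.7364 |
| 2,520 | satisfied | 0.7154 | 0.8025 |

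**Power to show both, independent outcomes.** Fixed rule: a₁a₂. Holm: b₁b₂ − (b₁ − a₁)(b₂ − a₂), that is, both below 0.05 and at least one below 0.025.

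- 3,300 replies: fixed 0.7658 × 0.8352 = 0.640. Holm 0.8429 × 0.8955 − 0.0771 × 0.0603 = 0.750.
- 2,520 replies: fixed 0.6372 × 0.7154 = 0.456. Holm 0.7364 × 0.8025 − 0.0992 × 0.0871 = 0.582.

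**Power per outcome under Holm, independent.** a₁ + (b₁ − a₁)a₂, and the same with the indices exchanged.

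- 3,300 replies: examined 77% to 83%, satisfied 84% to 88%.
- 2,520 replies: examined 64% to 71%, satisfied 72% to 77%.

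**Correlation 0.5** (simulation, 1,000,000 draws). Power for both rises from 68.6% to 77.7% at 3,300 replies and from 52.5% to 63.2% at 2,520, gains of about 9 and 11 points.

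**Other assumed effects.**

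- 50% to 55% on both outcomes, correlation 0 to 0.5: power for both rises from 54–60% to 67–71% at 3,300 replies, and from 37–45% to 49–56% at 2,520.
- 2 points on both (40% to 38%, 70% to 72%), independent, 3,300 replies: power for both rises from 2.4% to 4.7%.
- 10 points on both: power is already about 100%, so there is nothing to gain.
- Only one real effect: its power rises by (b − a) × 0.025, for example 0.0771 × 0.025 = 0.002 for examined at 3,300 replies.

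**At least one significant secondary outcome.** Both rules need a p-value below 0.025, so this probability is identical under the two.

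**Error rates.**

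- Both nulls true: the family-wise error is the same under both rules, 1 − 0.975² = 0.049 if independent and 0.046–0.047 in simulation at correlation 0.5.
- Exactly one null true, independent: the fixed rule gives 0.025. Holm gives 0.025 + 0.025 × a, with a the power of the other outcome. The lowest value is 0.025 + 0.025 × 0.6372 = 0.041 and the highest 0.025 + 0.025 × 0.8352 = 0.046.
- All three confirmatory tests: the bound is 0.05 + 0.025 + 0.025 = 0.10 now, and 0.05 + 0.05 = 0.10 with Holm on the pair.

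**The case against.** The strongest reply is that nothing here is wrong. A fixed 0.025 for each of two prespecified outcomes is simple and valid, contradicts nothing else in the document, and the plan promises no power for the secondary outcomes. That stands: this is a gain in efficiency, not the repair of an error.

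A reader might infer that the fixed rule buys nothing and that Holm is free in every sense. That goes too far. The two rules share the 5% bound for the pair, but the fixed rule also holds each outcome's own false-positive rate at 2.5%, and Holm gives that up when exactly one null is true. A check with both nulls true cannot show this, because there the two rules coincide. The missing gate matters here too. If the primary and one secondary are null while the other secondary is real, the chance of any false claim under independence goes from 1 − 0.95 × 0.975 = 7.4% to about 9%, still under 10%.

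A reader might also take the 11- to 13-point gain for both outcomes (independent case) as what this trial would obtain. The documents do not support that, because they give no secondary rates or effects. A benefit on both outcomes is not evident either: the Danish summary says that intervention parents must call again to reach a nurse or doctor, and the section on stopping early provides for a fall in satisfaction.

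Finally, 0.025 could be read as a joint level for the pair. The wording permits this, but a per-test level equal to 0.05/2 is the more natural reading.

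**Conclusion.** The point holds as an optional but worthwhile improvement. Two facts need no assumption about effects: Holm rejects everything the fixed rule rejects, and it keeps the pair's family-wise error at 5% or less under any correlation. It changes a result in one situation only, when one p-value is below 0.025 and the other lies between 0.025 and 0.05. The primary conclusion is untouched.

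The size of the gain depends on assumptions. It is about 9 to 13 points of power for showing both outcomes if each has the assumed 5-point effect and the correlation is between 0 and 0.5. It is about 2 points with independent 2-point effects, and close to zero if only one effect is real or both are large. The price is a higher realised error for a single true null, within the 5% bound.

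**What to change.** Replace the part of the Statistics sentence that sets the secondary threshold with:

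*The two secondary outcomes are tested with Holm's procedure at a family level of 0.05: the smaller p-value against 0.025 and, if significant, the larger against 0.05.*

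This costs one sentence and needs no extra families, data or recruitment time. It should be adopted before outcome data are seen by arm. The section Ethics and transparency plans an interim analysis of effect after 1,000 replies, so the change belongs before that look at the latest.

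The link between the primary and the secondary outcomes is a separate decision. This change neither settles it nor alters the 0.10 bound over the three tests.
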